DKEFS Color-Word Interference. This test measures processing speed in the control conditions of word reading and color naming, measures executive functions of inhibitory control in the interference condition, and cognitive flexibility in the switching condition. The interference condition is where the

color word names are written in a different ink color than the name. The switching condition is where the patient must switch back-and-forth between the response patters of naming the ink color and reading the word. The outcome measure for this task is the time to complete each of the four conditions.

Southwestern Assessment of Processing Speed (SWAPS). This is an assessment of processing speed. The patient is required to transcribe numbers to their corresponding written symbol as quickly as possible within 60 seconds. The outcome measure for this task is the total number of correct responses.

Subject safety monitoring: All HD-tDCS sessions will be overseen by the PI. All safety precautions recommended by scientific literature and the UT Southwestern IRB will be carefully followed. All adverse events volunteered by the subject or elicited by the research team will be recorded in the subjects' research file. All adverse events will be reported within one week to the IRB. Any severe adverse events will be reported within 24-48 hours to the IRB.

In order to safeguard our participants from a breach in confidentiality, the data is coded with a unique semi-random subject identifier (URSI). All data after initial entry into the study is coded based on the participant's number. A digital file containing completed questionnaires and assessments from the experimental session will be maintained with the URSI number. These files will be kept in an encrypted, IRB approved database (RedCap).

Statistical analysis: General linear models will be used to evaluate whether outcomes significantly change as a function of treatment allocation (sham, 1 mA HD-tDCS, 2 mA HD-tDCS). Changes from baseline on the outcomes of interest will be assessed. Participants with missing time points will not be excluded. All available data on all participants who 1) meet inclusion/exclusion criteria, 2) have been randomly assigned to groups, and 3) provide baseline data will be included regardless of whether they complete the trial.

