# Study sample:

The study sample will be limited to participants with a clinical diagnosis of AD.

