# Analysis Methods:

Two pairwise comparisons will be used to evaluate whether cognitive performance following the last treatment session statistically differs between HD-tDCS conditions, covarying for pre-treatment scores. This will consist of sham versus 1 mA and then sham versus 2 mA conditions. Eta effect sizes produced from the two comparisons will be transformed to Cohen's d and examined.

Clinically meaningful change associated with HD-tDCS will also be assessed. Proportions of individuals with a 5+ standardized score increase (T-score) on each measure of cognitive functioning will be characterized and evaluated. This will be completed examining sham versus 1 mA and then sham versus 2 mA conditions.

For the exploratory objective, those outcome measures identified to show significant changes immediately following the last treatment session (via statistical or Cohen's  $d \ge .50$ ) will be evaluated for this aim. Pairwise comparisons will be used to evaluate if scores at the 8-week follow-up statistically differ between HD-tDCS conditions (sham versus 1 mA; sham versus 2 mA), while covarying for the pre-treatment scores. Eta effect sizes produced from comparisons will be transformed to Cohen's d and examined.

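### The week-8 ANCOVA makes no use of the post-treatment score of anyone who misses week 8, although the protocol retains people who miss visits

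*SAP*

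**What the plan says.** **Protocol, Statistical analysis.** General linear models compare the three conditions: "Changes from baseline on the outcomes of interest will be assessed". On missed visits: "Participants with missing time points will not be excluded". Eligible, randomised participants who "provide baseline data will be included regardless of whether they complete the trial". No method for handling the missing scores is named.

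**SAP, Analysis Methods.** Sham is compared with 1 mA and with 2 mA, one visit at a time. The first pair of comparisons is to "evaluate whether cognitive performance following the last treatment session statistically differs between HD-tDCS conditions, covarying for pre-treatment scores". Only "those outcome measures identified to show significant changes immediately following the last treatment session" go forward to week 8, on statistical significance or a Cohen's d of at least .50. Then "Pairwise comparisons will be used to evaluate if scores at the 8-week follow-up statistically differ between HD-tDCS conditions", again with the pre-treatment score as the only covariate. The SAP calls this aim exploratory; the protocol lists it as a secondary objective.

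**SAP, Missing data.** The section covers only executive-function tests stopped because of impairment. It has no rule for a missed visit, no imputation, no repeated-measures model and no stated missing-data assumption.

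**The concern.** The persistence question concerns the same people at two follow-up times, and their scores at those times should be correlated. Someone who attends the post-treatment assessment and then misses week 8 has already shown how they responded. A week-8 ANCOVA on arm and baseline discards that.

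If those who leave are a response-related subset, and the subset differs between sham and active, the people left at week 8 are no longer comparable given baseline alone. The persistence estimate can then move in either direction, even though the score that would correct it is on file. Sham is the smallest arm under 1:2:2 allocation and serves both contrasts, so each sham score lost at week 8 affects both.

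**Working it through.** **1. Who enters which comparison.** This follows from the SAP's models when no imputation is specified.

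| Scores observed | Post-treatment ANCOVA | Week-8 ANCOVA |
|---|---|---|
| Baseline, post-treatment, week 8 | yes | yes |
| Baseline, post-treatment | yes | no; post-treatment score unused |
| Baseline, week 8 | no | yes |
| Baseline only | no | no |

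The second row is the point made here.

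**2. How bias arises.** The documents state no figure to reproduce, so all inputs below are assumed: unit SDs, a true effect of 0.50 SD at both follow-ups, and three sets of correlations (baseline-post / post-week 8 / baseline-week 8).

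Let β be the slope of week 8 on post-treatment score given baseline: β = (r_post,w8 − r_base,post × r_base,w8) / (1 − r_base,post²).

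- .5/.5/.4: (0.50 − 0.20)/0.75 = 0.40
- .7/.7/.6: (0.70 − 0.42)/0.51 = 0.549
- .8/.8/.7: (0.80 − 0.56)/0.36 = 0.667

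If dropout depends only on arm, baseline and post-treatment score, the week-8 ANCOVA has bias β × (δ_stay − 0.50). Here δ_stay is the baseline-adjusted post-treatment difference among those who stay. A model that also uses the post-treatment scores of those who leave replaces δ_stay by the difference in everyone assessed, which is 0.50, and the bias vanishes. That result is by construction.

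**3. Size.** Large-sample simulation; dropout is logistic in the observed change (post minus baseline), with the slope per SD of change. Ranges run over the three correlation sets. Entries are the week-8 ANCOVA estimate; the truth is 0.50.

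| Dropout | Slope 0.5 | Slope 1 | Slope 2 |
|---|---|---|---|
| One rule in both arms; sham 25%, active then about 10-21% | 0.49 | 0.47-0.48 | 0.43-0.46 |
| Poor responders leave sham only (25%); active 10% at random | 0.45-0.46 | 0.42-0.43 | 0.38-0.40 |
| Poor responders leave active only (25%); sham 10% at random | 0.54-0.55 | 0.56-0.58 | 0.60-0.62 |

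Using the post-treatment score gives 0.50 throughout. Check against step 2 for .7/.7/.6, slope 2, sham only: the ANCOVA gives 0.383, so δ_stay − 0.50 = (0.383 − 0.500)/0.549 = −0.21 SD.

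**4. Where there is no bias.** With poor responders leaving both arms at an equal 20%, the ANCOVA gives 0.50. A separate simulation in T-score units (true effect 5; correlations .70/.80/.65) gave bias within about 0.1 point for random dropout, and for a milder response-dependent rule shared by both arms. With low responders leaving the active arm only, bias was 0.3-0.4 points at 10% dropout and 1.15-1.25 at 30%.

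**5. Where the model helps little.** If dropout depends on the unseen week-8 score (sham 25%, active 10% at random, slope 2), the ANCOVA gives 0.23-0.33 and the estimate using the post-treatment score 0.25-0.37. At best that removes (0.365 − 0.328)/(0.500 − 0.328) = 22% of the bias, and at worst 9%. A second calculation gave 13-31%.

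**6. Pilot size.** Correlations .7/.7/.6, slope 2, sham-only dropout; root mean squared error (RMSE) of the week-8 estimate.

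| Sham/1 mA/2 mA | Pairwise ANCOVA: mean, RMSE | Three-arm model: mean, RMSE | Reduction in RMSE |
|---|---|---|---|
| 5/10/10 | 0.392, 0.531 | 0.502, 0.509 | 0.022/0.531 = 4% |
| 10/20/20 | 0.384, 0.371 | 0.496, 0.349 | 0.022/0.371 = 6% |

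The bias is 0.108/0.520 = 0.21 and 0.116/0.352 = 0.33 of a standard error. In a second run at 5/10/10, RMSE was 0.538 for the pairwise ANCOVA, 0.526 for a three-arm ANCOVA and 0.514 for the three-arm model, so half the gain there comes from the third arm. Under one rule in both arms the reductions are smaller: 0.519 to 0.506 (2.5%) and 0.354 to 0.349 (1.4%).

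**The case against.** The strongest reply is that there is no departure from the protocol. An ANCOVA run on whoever has a score at each visit uses every score observed at that visit and removes nobody from the visits they attended. The protocol promises no imputation or longitudinal model, and its own change-from-baseline analysis has the same limit. This largely stands. A reader might infer that the SAP breaks the protocol's inclusion rule or restricts the analysis to completers; the text supports neither. What remains is narrower: at week 8 a collected, relevant score goes unused.

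Second, participants and the assessors other than the PI are blinded, so strongly response-driven dropout in one arm only is an extreme case. That also stands, and the one-rule row deserves more weight than the one-arm rows.

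Third, a new model for a gated, exploratory aim in an unpowered pilot may seem disproportionate, and two week-8 answers without a stated priority would be worse than one. The remedy must therefore be confined to week 8 and say which estimate leads.

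Two other readings should be set aside. Loss of baseline-only participants looks serious, but they add almost nothing to an arm contrast under any likelihood model. The sample restriction, "The study sample will be limited to participants with a clinical diagnosis of AD", is a separate matter from missed visits.

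**Conclusion.** The point holds as a minor one. The SAP's week-8 estimate ignores the post-treatment score of participants who miss week 8, and a standard model would use it.

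Under the assumed inputs, a true 0.50 SD would be estimated at about 0.43-0.49 with one dropout rule in both arms, and at 0.38-0.46 if only sham dropout is response-driven. The direction reverses if active loses its poor responders. A reader might infer from these figures that the week-8 result is biased. The documents do not support that: they give no sample size, dropout rate or correlations, and under random, baseline-dependent or arm-equal dropout the planned ANCOVA is adequate.

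The stakes are limited because the SAP treats week 8 as exploratory and tests only measures that pass the post-treatment gate. At pilot size, sampling error is several times the bias.

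**What to change.** For the week-8 contrasts (sham versus 1 mA, sham versus 2 mA):

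- **Main estimate.** Replace the single-visit ANCOVA with one likelihood-based repeated-measures model per outcome on all three arms and visits. Put baseline in the outcome vector or use it as a covariate, with arm-by-visit terms and unstructured covariance.
- **Fallback.** If the model does not converge, use multiple imputation that includes arm, baseline and post-treatment score.
- **What stays.** Keep the pairwise ANCOVA at post-treatment for eta-squared, Cohen's d and the d ≥ .50 gate. Keep it at week 8 as a supporting available-case analysis, named as secondary to the model.
- **Labelling.** The SAP's Design section describes the assessments in the past tense. If data have been seen, label the model as added after data collection.

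Optional clarifications, which are not the basis of this point: report missingness by arm and visit, and state the denominator for the responder analysis ("Proportions of individuals with a 5+ standardized score increase (T-score) on each measure of cognitive functioning will be characterized and evaluated").

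**Cost.** A SAP paragraph and modest programming for up to 15 measures (2 + 2 + 3 + 4 + 4); no new data. The model may fail to converge at small N. Total error falls only about 4-6% in the sham-only case and less under a common dropout rule, with part of the gain due to the third arm. Protection is slight if dropout depends on the unseen week-8 score.

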#### Missing data:

In the event few scores of executive function are available (due to tests being discontinued from cognitive impairment), alternative indices will be derived and examined post-hoc. Number of items not completed when the time limit is reached will be summed (higher scores representing lower performance) for TMT B, DKEFS Inhibition, and DKEFS Inhibition/Switching measures. Scores will be examined in ANCOVA models and effect sizes, but not as indices for clinically meaningful change.

#### Multiple comparison correction:

Statistical significance will be set at p < 0.05 with no correction for multiple comparisons to reduce the chances of a Type II error given the small sample size of the pilot study.
